Participants: 110 patients (55 per group) with PD-MCI will be recruited for this study as well as 110 identified and consistent caregivers of the participants. All caregivers will be asked to complete several questionnaires regarding the participant's quality of life and daily functioning prior to the intervention, at follow-up visits, and after the intervention. Although attrition did not occur in Phase I, over-recruitment by 20% will be instituted to account for possible subject attrition or unusable data. Participants will receive a payment of \$40 for each of the four assessments they complete (pre- and post-intervention/support and 6- and 12-month follow-ups).

Procedures: We will primarily recruit Veterans with PD from the VASDHS Neurology and Neuropsychology Clinics. While we will attempt to exhaust recruitment at VA clinics first, recruitment of women may be limited at the VA, and therefore, we will likely need to recruit from outside clinics to obtain a PD-epidemiologically accurate gender ratio of 60 (men)/40 (women). In this regard, we will primarily recruit from the University of California, San Diego (UCSD) Movement Disorders Center. Referred participants will be screened for inclusion/exclusion criteria (please see above) and consented if appropriate. All participants will have Level II MDS-criteria based diagnosis of MCI derived from a formal neuropsychological evaluation within the past 12 months. As most participants will be referred from the VASDHS and UCSD Movement Disorder Center, the majority will have MDS-criteria MCI diagnoses prior to referral. However, should a PD patient be referred for this study who has not had formal neuropsychological testing or if testing is outdated (>12 months), pre-inclusion neuropsychological testing will be performed through [name] lab, which follows patients neuropsychologically. Likewise, if the WRAT-4 Reading scale has not been administered within the past year, this 2-5 minute measure will also be administered to ensure adequate reading level. To avoid confounds, no test proposed as outcome measures in this study will be used to determine the PD-MCI diagnosis.

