Upon meeting study criteria, participants will be randomized to one of two 10-week conditions (CogSMART-PD or Supportive Care). Randomization will occur in blocks (i.e., first 5 people enrolled will be assigned to the intervention group, next 5 will be assigned to control group, next 5 will be assigned to the intervention group, and so on until the sample size of 55 per group is met). Within one to 1.5 weeks prior to beginning the group, participants will be tested by a research assistant blinded to group assignment on a 2-2.5 hour

battery of cognitive, neuropsychiatric, health status/QoL, and strategy use measures as well as a motor assessment (UPDRS-Part III), which will immediately precede the cognitive assessment (please see Assessment/Materials). Participants will be tested in the “on-state” of parkinsonian medications to limit confounding variability (e.g., of motor symptoms, such as tremor) on test results. All participants will be tested at the same time, preferably in the morning, if possible. Breaks will be given during the assessment as needed. Groups will consist of 5 individuals with PD-MCI and be led by a trained clinician (who is not involved in the clinical care or assessment of these participants). Following the intervention and 6- and 12-months post-intervention, PD-MCI participants will be re-tested by a group-blinded research assistant. 24 months post-intervention, participants will be asked to complete a brief (15 minute) telephone interview regarding changes in health status or living situation since the 12-month follow up. Following the 12-month follow-up, the control (support) group will be permitted to join CogSMART-PD.

Assessment/Materials: Outcome measures were carefully selected so that they: 1) represent areas that are frequently impaired, dysfunctional, or problematic for individuals with PD-MCI; 2) correspond to domains that are targeted for improvement by the CogSMART-PD intervention; 3) have adequate psychometric properties for use in PD; and 4) have shown utility and applicability based on the pilot and preliminary studies. Total neuropsychological and motor testing time is estimated to be 2-2.5 hours.

Cognitive Function and Cognitive Strategy Assessment:

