The Unified Parkinson's disease Rating Scale - Part III (UPDRS-Part III)^{75, 76} and the modified Hoehn and Yahr Rating Scale (HYRS)^{77, 78} will be used to assess level of motor impairment and disease severity. For this assessment participants go through a series of tasks designed to assess various motor characteristics such as speech, facial expression, rigidity, finger tapping, hand movements, toe tapping, freezing of gait, balance, etc. We will also use UPDRS item #13 to assess fall risk (please see Monitoring Plan below). These are standard instruments for measuring the motor symptoms and disease severity in patients with PD and have been used extensively in both research and clinical settings. VASDHS/UCSD neurologists will perform these assessments immediately prior to the cognitive assessment at the pre and 12-month follow up evaluations.

Adjunct Performance Measures:

Motor Skill Fitness measures will be carried out by a trained research assistant at the VA Medical Center

Subjects will undergo body mass index analysis at the VA Medical Center

De-identified data from these Motor Skill Fitness measures will be analyzed in the Smart Lab at UC San Diego. No participant data will be collected there.

Client Satisfaction with the intervention will be assessed at the end of the intervention with the Client Satisfaction Questionnaire (CSQ-8)⁷⁹. The CSQ-8 is an 8-item, 2-3 minute measure that yields a single score, ranging from 8 to 32 (each item rated on a 4-point Likert scale), with higher scores indicating greater satisfaction. The CSQ-8 has been widely used in clinical research trials and is reported to have excellent reliability and internal consistency, acceptability to clients and service providers, and sensitivity to different levels of program quality.

Intervention: The treatment intervention is CogSMART-PD. Participants will meet in groups of 5 individuals per group for 1.5 hours once per week for 10 weeks.

Control Group: The supportive care (control) group will entail having groups of 5 individuals with PD-MCI meet for peer-support for 1.5 hours once per week for 10 weeks. A trained clinician will serve as the facilitator of this group and will be instructed to not provide any treatment or intervention strategies. The main role of the facilitator will be to create a safe and respectful environment where members feel comfortable sharing their knowledge and insight with each other.

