Data Analysis: Preliminary analyses will begin with an examination of the distribution of variables to assess their characteristics (means, standard deviations, skewness), to provide descriptive statistics of the study population, and to allow assessment of randomization. Continuous measures will be tested for normality and homogeneity of variance. Non-normally distributed variables will be transformed to meet the normal distribution assumption for linear effects models. Analyses will include tests of randomization and comparability across conditions. Randomization will be tested by performing a series of t-tests and chi-square tests to compare the groups on demographic and initial clinical variables. Pre-specified baseline variables including age, education, gender, severity and duration of illness, and motor symptoms will be considered as potential covariates (as fixed effects) in the multivariate analyses. Any other variables (e.g., baseline cognition as assessed by the MoCA, medications) on which the groups differ initially will also be explored as covariates in subsequent analyses, as described below. In the case of missing data, appropriate data analytic techniques will be used, which may include deletion, imputation, inclusion of an indicator of missing values, or pattern-mixture modeling. Outcomes will be analyzed using SPSS release 16 (SPSS, 2007), and open source statistical software R⁸¹.

As an exploratory aim, we will recruit 60 additional individuals to complete the protocol as described above and in addition, participate in two (pre/post) hour-long brain imaging (fMRI) sessions. The imaging sessions will consist of a structural brain scanning and participation in an fMRI cognitive task (please see below). Following the baseline evaluation, half of the participants will be randomly assigned to the intervention group ($n = 30$) and participate in the CogSMART program. The groups will be broken up to consist of approximately 5 individuals. The remaining participants ($n = 30$) will be assigned to the non-intervention/control ("supportive care") group. This group will also be broken down into groups of 5 when enrolled in the intervention. Participants will be retested by a group assignment-blinded examiner on the clinical and cognitive battery and imaging protocol following the intervention or waitlist.

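### Phase II delivers both arms in therapy groups of five, but no outcome model is written out and no group term is named; with independent group effects, a model fitted on the stated terms alone understates the standard error

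*Combined protocol and SAP*

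**What the plan says.** All references are to Phase II of the combined protocol and SAP.

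- **Size** (Section 9, Participants): "110 patients (55 per group) with PD-MCI will be recruited for this study". Over-recruitment of 20% is planned for attrition or unusable data. The text does not say whether 110 already includes it.
- **Allocation** (Section 9, Procedures): "first 5 people enrolled will be assigned to the intervention group, next 5 will be assigned to control group", alternating until each arm is full.
- **Delivery** (Section 9, Procedures): "Groups will consist of 5 individuals with PD-MCI and be led by a trained clinician".
- **Intervention arm** (Section 9, Intervention): "Participants will meet in groups of 5 individuals per group for 1.5 hours once per week for 10 weeks".
- **Control arm** (Section 9, Control Group): "groups of 5 individuals with PD-MCI meet for peer-support for 1.5 hours once per week", with a clinician as facilitator.
- **Analysis** (Section 9, Data Analysis): non-normal variables "will be transformed to meet the normal distribution assumption for linear effects models". Baseline patient characteristics "will be considered as potential covariates (as fixed effects) in the multivariate analyses". Other variables on which the arms differ at baseline "will also be explored as covariates in subsequent analyses, as described below".

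Missing-data options and software come next, and then the text turns to the fMRI aim. The analyses to which the last quote points do not appear. The text names no therapy-group, block or facilitator term, no ICC and no design effect.

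**The concern.** Ten weekly sessions with the same few peers and the same leader can make outcomes alike within a therapy group. This applies to both arms, since the control condition is peer support. The runs used for allocation are the same size as the therapy groups. If each run forms one group, clustering is therefore in the allocation as well as the delivery.

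An analysis that treats the patients in an arm as independent then attributes too much information to them. The between-arm p-value would be too low for the primary outcome (Matrix Reasoning at 10 weeks; Section 6, Aim 1) and for the secondary between-arm comparisons. If the error structure is left open until the data are in, the choice can also be made after its effect on the p-value is known.

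**Working it through.** **Inputs from the documents.** 55 patients per arm and therapy groups of five in both arms, so 55 / 5 = 11 groups per arm. If the 20% comes on top of 110, then 110 × 1.2 = 132 are recruited, 66 per arm, and 66 / 5 = 13.2, or about 13 groups per arm.

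**Assumptions.** The documents state no alpha, power, effect size, SD or ICC for Phase II, so the figure of 110 cannot be reproduced. I assume a two-sided 5% test, an unadjusted comparison, independent group effects, and ICC 0.01 / 0.02 / 0.05 / 0.10.

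**Formulas.** With m analysed patients per group, the design effect is DE = 1 + (m − 1) × ICC. The true standard error is √DE times the one reported without a group term. True type I error is approximately 2 × [1 − Φ(1.96 / √DE)].

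Worked case, m = 5 and ICC 0.05: DE = 1 + 4 × 0.05 = 1.20; √DE = 1.095; 1.96 / 1.095 = 1.79; error = 7.4%.

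**Uneven loss.** If each of five members is lost with probability 0.2, the mean group size is 4 and its variance is 5 × 0.8 × 0.2 = 0.8. The effective size is (4² + 0.8) / 4 = 4.2, so DE = 1 + 3.2 × ICC. This does not depend on the number of groups, so 11 and 13 groups per arm give nearly the same answer.

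**Type I error without a group term** (simulated):

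| Case | ICC 0.01 | 0.02 | 0.05 | 0.10 |
|---|---|---|---|---|
| m = 5: DE | 1.04 | 1.08 | 1.20 | 1.40 |
| m = 5: √DE | 1.02 | 1.04 | 1.10 | 1.18 |
| m = 5: type I error | 5.5% | 6.0% | 7.4% | 9.8% |
| m = 4: type I error | 5.4% | 5.7% | 6.8% | 8.6% |
| 20% random loss, 11 or 13 groups per arm: type I error | 5.4% | 5.7% | 6.9% | 8.9% |

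The m = 5 row is a ceiling: it assumes no attrition and that no patient is dropped for a medication change (Section 10, exclusion criteria). In the same simulations a t-test on group means has size of about 5%.

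**Smooth enrolment drift.** Suppose the within-group correlation comes only from a linear trend in who enrols. Alternating runs nearly balance such a trend. The test without a group term then stays near 5%, while the group-mean test becomes conservative (about 4.4 / 4.1 / 3.1 / 1.8%).

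**Power of the remedies.** With 55 independent patients per arm and 108 df, 80% power corresponds to a difference of 0.539 SD. At that difference, with 11 full groups per arm and 22 − 2 = 20 df:

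| Method | ICC 0 | 0.01 | 0.02 | 0.05 | 0.10 |
|---|---|---|---|---|---|
| Group means: power | 77% | 75% | 74% | 69% | 62% |
| Group means: size | 5.0% | 5.0% | 5.0% | 5.0% | 5.0% |
| REML random intercept: power | 73% | 72% | 71% | 68% | 62% |
| REML random intercept: size | 3.2% | 3.4% | 3.6% | 4.1% | 4.6% |

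Part of the loss comes from the 20 df alone, as the ICC 0 column shows.

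**The case against.** **The plan does not say that groups will be ignored.** A reader might infer that it does, or that the primary test really runs near 10%. The documents support neither inference. Naming linear effects models, with covariates entered as fixed effects, is compatible with a mixed model whose random part was left unwritten. What stands is the omission. Even a mixed model with a patient effect for repeated visits would not account for therapy groups.

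**The effect on the primary outcome may be trivial.** Matrix Reasoning is a performance test given by a blinded assistant, so its ICC may be lower than that of mood or quality-of-life scales. Section 9.11 describes a treatment manual, clinician training and audio-rated fidelity, which should limit variation between CogSMART-PD groups. At ICC 0.01 to 0.02 the excess is 0.5 to 1.0 percentage points, and the REML remedy (size 3.4 to 3.6%) is then further from 5% than the test it replaces. This objection stands, and it is why the two remedies are not interchangeable.

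**A positive ICC is not enough by itself.** The error is inflated by independent group effects, not by smooth enrolment drift under alternation. This narrows the point but does not remove it, because shared leaders, peers and sessions can produce independent effects.

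**The figures rest on assumptions.** They are unadjusted, whereas Hypothesis 1 concerns improvement and covariates are planned. The ICC of a baseline-adjusted outcome could differ.

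**The wider gap is that no Phase II outcome model exists at all.** That is true, and the group term belongs in the same repair.

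**Conclusion.** The point holds as a conditional gap in specification, and it should be fixed. The omission is certain from the text. Its consequence needs two conditions: independent group effects, and a model fitted with only the stated terms. Its size depends on an ICC that the documents do not give. With the planned 20% loss, type I error runs from 5.4% at ICC 0.01 to 8.9% at ICC 0.10; 9.8% is the ceiling with full groups. The inflation is small at ICC 0.01 to 0.02, which may be the range for the primary outcome, and material from about 0.05.

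A reader might also conclude that 110 patients are too few because no design effect was applied. The documents do not support that, since no power target is stated against which to judge 110.

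**What to change.** In Section 9, Phase II, Data Analysis, write out the primary and secondary between-arm models and name one of these methods in advance:

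1. **Random intercept for therapy group in both arms.** Group must not be a fixed effect, which would be aliased with arm. Use small-sample degrees of freedom based on the groups actually formed (20 for 11 per arm, 24 for 13 per arm). Add a patient-level random effect where the 6- and 12-month repeated measures are modelled.
2. **Group-mean analysis.** This holds size closer to 5% when the ICC is low.

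Under either method, classify each patient by the group first assigned. For anyone who rejoins a later group, which Section 14 allows, this is an approximation. Report the ICC for each outcome.

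The cost is one or two sentences when the model is written. No new data are needed: Section 9.11 already provides for a key linking group numbers to individuals, which must be kept until the analysis is done. The price is wider intervals and the loss of power tabulated above. If the correlation comes only from enrolment drift, the group-mean test is also conservative.

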Monitoring Plan. As individuals with PD are at high risk for falls, we will carefully screen all individuals for history of falls upon recruitment. We will use the baseline UPDRS falling item (#13) in which a history of falls is categorized on a likert scale from 0 (none) to 4 (falls >once per day). A history of falls as assessed by the UPDRS appears to be one of the best predictive methods of subsequent falls at this time⁸⁰. Those individuals who endorse a history of falling or score >0 on the UPDRS falling item, will be closely monitored. This includes ensuring that they are escorted to and from the intervention room from their vehicle as well as to and from the bathroom, as needed. Should a patient need help within the bathroom,

a caregiver will be requested to assist. If needed, we will utilize the VA escort service. Although not common in PD, all participants will also be assessed for suicidal ideation/intent at baseline, as standard of care for psychological/behavioural interventions. If suicidal ideation is acknowledged, indicated by a score of 2 or greater on item 9 of the Beck Depression Inventory-II (BDI-II), research participants will be referred directly to a VA-privileged clinician for further evaluation. These participants will be monitored for changes in mood during the intervention.

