Test anxiety, boredom and fatigue will be minimized by explaining the testing procedures, by supportive assurance, and by taking brief rest periods throughout the two-2.5 hour evaluation. Evaluations will be performed by examiners experienced in working with geriatric and neurologic populations and will be able to gauge when breaks are needed or when testing may need to be rescheduled or cancelled due to severe fatigue or anxiety. To minimize potential discomfort during the UPDRS motor exam, study staff will briefly explain the nature and purpose of the exam before beginning, and will instruct subjects to ask questions or communicate if they are unsure about or uncomfortable with any portion of the exam. Additionally, subjects will sign and receive a copy of the consent addendum, which has further details about the exam, prior to the exam. Each CogSMART-PD session will last approximately 1.5 hours and breaks are offered throughout the session as well. As individuals with PD are at a high risk for falls, we will carefully screen all individuals for history of falls upon recruitment. We will use the baseline UPDRS falling item (#13) in which a history of falls is categorized on a likert scale from 0 (none) to 4 (falls >once per day). A history of falls as assessed by the UPDRS appears to be one of the best predictive methods of subsequent falls at this time. Those individuals who endorse a history of falling or score >0 on the UPDRS falling item, will be closely monitored. This includes ensuring that they are escorted to and from the intervention room from their vehicle as well as to and from the bathroom, as needed. Should a patient need help within the bathroom, a caregiver will be requested to assist. If needed, we will utilize the VA escort service. Although not common in PD, all participants will also be assessed for suicidal ideation/intent at baseline, as standard of care for psychological/behavioural interventions. If suicidal ideation is acknowledged, indicated by a score of 2 or greater on item 9 of the Beck Depression Inventory-II (BDI-II), research participants will be referred directly to a VA-privileged clinician for further evaluation. These participants will be monitored for changes in mood during the intervention.

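### Phase II escorts rest on fall history taken before the sessions start; no visible text schedules a question about new falls during the 10 weekly sessions

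*Combined protocol and SAP*

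**What the plan says.** The Monitoring Plan (Section 9, Phase II) treats people with Parkinson's disease as a high-risk group for falls and finds those who need help in two ways. One is a history: "we will carefully screen all individuals for history of falls upon recruitment". The other is a rating: "We will use the baseline UPDRS falling item (#13) in which a history of falls is categorized on a likert scale", running from 0 (no falls) to 4 (more than one a day). The trigger is: "Those individuals who endorse a history of falling or score >0 on the UPDRS falling item, will be closely monitored". The precaution includes "ensuring that they are escorted to and from the intervention room from their vehicle as well as to and from the bathroom, as needed". The Phase II parts of Section 14 (Potential Risks) and Section 15 (Risk Management) repeat the rule.

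The timing also comes from Section 9, Phase II. Under Procedures: "Within one to 1.5 weeks prior to beginning the group, participants will be tested by a research assistant blinded to group assignment". Both arms then meet once a week for 10 weeks. Afterwards, "Following the intervention and 6- and 12-months post-intervention, PD-MCI participants will be re-tested by a group-blinded research assistant". The paragraph headed PD Motor and Disease Severity Assessment names item 13 as the fall-risk measure, points to the Monitoring Plan, and gives the schedule: "VASDHS/UCSD neurologists will perform these assessments immediately prior to the cognitive assessment at the pre and 12-month follow up evaluations".

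For the exploratory Wii and Odoroki programmes, Sections 14 and 15 have participants sit if the medical chart marks them as likely to fall. No update of that information during the programme is described.

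**The concern.** The Monitoring Plan justifies its rule by saying that past falls are among the best available predictors of later ones. On that reasoning, a first fall in week 4 is exactly the information the rule needs, yet no scheduled step collects it. The person concerned may go on walking between car and session room without the escort the protocol would have given had the fall come a month earlier.

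The plan does provide continuing checks elsewhere. Participants with suicidal ideation are followed for mood during the intervention (Monitoring Plan), and medications are recorded at each testing session (Section 10, Phase II exclusion criteria). The form's own prompt for Section 15 asks, where applicable, how often safety data are collected. For falls, the Phase II answer names only recruitment and baseline.

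What is at stake is participant safety. The comparison of Matrix Reasoning at 10 weeks does not depend on it.

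**Working it through.** The plan states no figure on this point, so the check sets the schedule out by time point and then works out the window and the cost of closing it.

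**1. Falls checks by time point (Section 9, Phase II)**

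- Recruitment: fall history asked.
- Baseline, 1 to 1.5 weeks before the first session: item 13 rated (taking the baseline rating to be made at the pre-intervention evaluation).
- Weekly sessions 1 to 10: none stated.
- Post-intervention visit: none stated.
- 6-month visit: none stated.
- 12-month visit: the assessments with which item 13 is described are repeated, long after the sessions have ended.

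**2. Could another listed item fill the gap?**

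- The Modified Falls Efficacy Scale appears in Section 9.8 with no visits and no action threshold. Its cited reference concerns fear of falling.
- The weekly participant and clinician evaluations in Section 9.11 belong to the treatment-fidelity plan. Falls are not mentioned.
- Close monitoring under the trigger applies to people who have already been flagged.

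**3. Length of the window.** Baseline testing to the end of ten full weeks of sessions is 1 + 10 = 11 weeks at the shortest and 1.5 + 10 = 11.5 weeks at the longest.

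**4. How many people.** The number missed would be (110 − F) × p × m, where 110 comes from Section 9 ("110 patients (55 per group) with PD-MCI will be recruited for this study"), F is the number flagged at recruitment or baseline, p is the chance that an unflagged person first falls in the window, and m is the chance that staff do not learn of it. The documents give none of F, p or m, so the calculation stops there.

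**5. Cost of asking.** The 15 to 30 seconds per question is an assumption.

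- Main sessions: 110 × 10 = 1,100 questions. 1,100 × 15 s = 16,500 s = 4.6 h; 1,100 × 30 s = 33,000 s = 9.2 h.
- If the 20% over-recruitment comes on top of 110: 132 × 10 = 1,320 questions, or 5.5 to 11 h.
- Adjunct programmes, with 8 to 10 people each, reading the Wii text as ten half-hour sessions, and assuming none share a day with the weekly group: Wii 80 to 100 questions, Odoroki (20 sessions) 160 to 200, together 240 to 300. 240 × 15 s = 1 h; 300 × 30 s = 2.5 h.

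**The case against.** The best defence is that the trigger sentence carries no time limit. Only the item 13 rating is tied to baseline. A person who reports a fall in week 4 has endorsed a history of falling and meets the trigger as written, and escorts are given as needed. A trained clinician leads every group of five, caregivers complete questionnaires on daily functioning, and the chart already informs the adjunct programmes. The threshold is the lowest possible, baseline is at most 1.5 weeks before the first session, and the sessions are over ten weeks later. On this view, a scheduled question is one reasonable preference among several.

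Much of this stands. A reader might infer that a later faller is picked up only by volunteering the fact. The documents do not support that, because staff may see a fall or hear of it from a caregiver, and nothing stops them from adding the person. What remains is that none of these routes is a scheduled falls question, so detection is left to chance.

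Two further limits apply. Parts of the form are not in the public text, the tick-boxes on safety monitoring cannot be read, and the content of each retest visit is not itemised. The absence is therefore an absence from the visible text. The escort wording also names the intervention room and bathroom, so the post-intervention and 6-month assessment visits are secondary. So is return to a later group, which Section 14 already leaves to individual judgement.

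**Conclusion.** The point holds as a minor one and a cheap improvement. The Phase II escort rule is fed by information gathered before the sessions begin, and no visible text schedules an update during the 10 weeks in which escorts are mainly given. Those exposed are participants not flagged at baseline who first fall in that window and whose fall does not reach staff.

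Three stronger conclusions may tempt a reader, and the documents support none of them:

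- That protection lapses for over a year. The interval between item 13 ratings is indeed 1 + 10 + 52 = 63 to 1.5 + 10 + 52 = 63.5 weeks, but the sessions for which the escort is written end at 11 to 11.5 weeks.
- That all 110 participants, or some stated number of them, go unprotected. Those flagged at baseline already have the precaution, and a count of the rest needs quantities the plan does not give.
- That falls go unrecorded as adverse events. The visible text does not settle this either way.

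The reading assumes that the 12-month schedule in the motor-assessment paragraph covers item 13, which that paragraph introduces.

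**What to change.** At each weekly session in both arms, and at each Wii or Odoroki session, the facilitator asks one question: 'any fall since last visit?' The existing escort trigger, and the seating rule in the adjunct programmes, are then applied to the most recent answer. The same question is asked when a participant rejoins a later group. Asking in both arms keeps contact equal, and the facilitator takes no part in outcome assessment, so blinding is not touched.

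The question may also be put at the post-intervention and 6-month visits, but this is optional. If it is, a yes/no answer is enough and avoids detail that could reveal the arm to the blinded research assistant.

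The cost is a few lines of protocol text, the staff hours worked out above, and a few more escorts. No neurologist rating is added, and the outcome schedule and the primary analysis stay as they are.
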